4.2 Randomization

Eligibility should be verified again before randomization. Eligible and consenting patients will be randomized by certified research staff using an internet based randomization system maintained by the BCC. Randomization will occur when the patient is from 38 weeks 0 days to 38 weeks 6 days of gestation. The patient will be assigned either to the induction of labor group or the expectant management group.

If the patient has had a digital cervical exam within the past 72 hours, and all components of the modified Bishop score are documented (cervical dilation, cervical effacement or cervical length, and fetal station), randomization may be done in person or over the telephone. If the patient has not had a digital cervical exam within the past 72 hours, or if components of the modified Bishop score are not documented, she must be randomized in person and have a digital cervical exam within that same day.

4.3 Baseline Procedures

In addition to information collected for eligibility, project gestational age, and project EDC determination, the following information will be obtained at randomization from a patient interview followed by a review of her chart:

- Components of the modified Bishop score: cervical dilation, cervical length or effacement, and fetal station from digital cervical exam
- Demographic information: age, race, ethnicity, insurance status
- Medical history: first clinic weight, current weight, height, chronic disease history
- Obstetrical history including outcome(s) of any prior pregnancies
- Social history: marital status, alcohol use, and tobacco use
- Current pregnancy complications

4.4 Study Procedures

Women randomized to induction of labor will undergo induction via oxytocin at 39 weeks 0 days to 39 weeks 4 days. Those with an unfavorable cervix (modified Bishop score < 5) will first undergo cervical ripening (method left to the discretion of the patient's physician) in conjunction with or followed by oxytocin stimulation unless a contraindication arises.

Women randomized to expectant management will have at least weekly follow-up visits with their providers and, unless a medical indication is present, will continue pregnancy until at least 40 weeks 5 days of gestation. Antepartum fetal testing will be initiated no later than 41 weeks 6 days according to policies at each center. All patients will undergo induction via oxytocin by 42 weeks 2 days.

4.5 Patient Management and Follow-up

Patients in the induction of labor group (as well as patients in the expectant management group that undergo induction of labor) should be allowed adequate time to labor before considering the induction "failed" and proceeding to cesarean section. An induction will be considered "failed" if at least 12 hours have elapsed since both rupture of membranes and use of a uterine stimulant and the patient remains in latent labor. It is expected that the fetal heart rate will be monitored while the patient is being induced (including ripening) and during labor and that patients will stay in the hospital until delivery once the induction (including ripening) is started. Mechanical ripening using a Foley catheter without saline infusion is permitted without monitoring and may be used in an outpatient setting according to policies at each center.

For patients in the expectant management group, only a valid medical indication should warrant delivery before 40 weeks and 5 days. Otherwise, no attempt will be made to alter or mandate clinical management of the subjects.

Women will be asked about pain experienced during childbirth and asked to complete a questionnaire on feelings of control during childbirth. All women will be contacted at six weeks postpartum to determine unanticipated outpatient or inpatient visits for them or their infants since discharge and to complete the same questionnaire about feelings of control again.

4.6 Adverse Event Reporting

Detailed information concerning adverse events will be collected and evaluated throughout the conduct of the protocol.

The NICHD Project Scientist and the BCC will be notified within seventy-two hours of any maternal death, perinatal death, or life-threatening maternal event by email/phone/fax, if the event occurred in a MFMU Network hospital. For any maternal death, perinatal death, or life-threatening maternal event occurring outside a MFMU Network hospital, the adverse event must be reported to the NICHD and the BCC within twenty-four hours of being notified. These and other adverse events deemed serious, unexpected and definitely, possibly or probably related, will be immediately (within twenty-four hours of notification) forwarded by the BCC to the DSMC Chair, NIH representative, and any other DSMC member who requests notification. If a death is reported, a copy of the patient's medical record will be made.

Adverse events which do not qualify under the above definition must be reported to the BCC within 7 days of being notified. These adverse events will be collected and sent to the Chair, NIH representative, and any other requesting DSMC member on a monthly basis. The Chair decides whether the adverse event reports should be disseminated to the rest of the committee, and whether a follow-up call or meeting is required. NICHD representatives may also request follow-up of specific events. All adverse events will be considered along with other interim safety data in the DSMC deliberations.

4.7 Study Outcome Measures and Ascertainment

4.7.1 Primary Outcome

The primary outcome is a composite of severe neonatal morbidity and perinatal mortality (any one of the following):

- Antepartum, intrapartum, or neonatal death
- Intubation, continuous positive airway pressure (CPAP) or high-flow nasal cannula (HFNC) for ventilation or cardiopulmonary resuscitation within first 72 hours
- Apgar ≤ 3 at 5 minutes
- Neonatal encephalopathy as defined by Shankaran et al.⁴⁹
- Seizures
- Sepsis. The diagnosis of sepsis will require the presence of a clinically ill infant in whom systemic infection is suspected with a positive blood, CSF, or catheterized/suprapubic urine culture; or, in the absence of positive cultures, clinical evidence of cardiovascular collapse or an unequivocal X-ray confirming infection.
- Pneumonia confirmed by X-ray or positive blood culture.
- Meconium aspiration syndrome
- Birth trauma (bone fractures, brachial plexus palsy, other neurologic injury, retinal hemorrhage, or facial nerve palsy)
- Intracranial hemorrhage (intraventricular hemorrhage grades III and IV, subgaleal hematoma, subdural hematoma, or subarachnoid hematoma)
- Hypotension requiring pressor support

4.7.2 Maternal Secondary Outcomes

1. Cesarean delivery and indication
2. Incisional extensions at cesarean section, including J shape or T shape; or cervical traumas
3. Operative vaginal delivery and indication
4. Chorioamnionitis, defined as a clinical diagnosis before delivery
5. Third or fourth degree perineal laceration
6. Maternal death
7. Admission to intensive care unit (ICU)
8. Preeclampsia/gestational hypertension
9. Postpartum hemorrhage, defined as any of the following:
 - Transfusion
 - Non-elective hysterectomy
 - Use of two or more uterotonics other than oxytocin
 - Other surgical interventions such as uterine compression sutures, uterine artery ligation, embolization, hypogastric ligation, or balloon tamponade
 - Curettage
10. Interval from randomization to delivery
11. Gestational age at delivery
12. Maternal postpartum infection, defined as any of the following:
 - Clinical diagnosis of endometritis
 - Wound reopened for hematoma, seroma, infection or other reasons
 - Cellulitis requiring antibiotics
 - Pneumonia
 - Pyelonephritis
 - Bacteremia unknown source
 - Septic pelvic thrombosis
13. Maternal venous thromboembolism (deep venous thrombosis or pulmonary embolism)

4.7.3 Fetal and Neonatal Secondary Outcomes

1. Birth weight
2. Duration of respiratory support including ventilator, CPAP, high-flow nasal cannula (HFNC)
3. Cephalohematoma
4. Shoulder dystocia
5. Transfusion of blood products or blood
6. Hyperbilirubinemia requiring phototherapy or exchange transfusion

7. Hypoglycemia (glucose < 35 mg/dl) requiring IV therapy
8. Admission to neonatal intensive care unit (NICU) or intermediate care unit

4.7.4 Utilization of Medical Resources

1. Number of hours on the labor and delivery unit
2. Maternal postpartum length of hospital stay
3. Neonatal length of hospital stay

5 Statistical Considerations

5.1 Data Relevant to the Primary Outcome

To estimate the rate of the primary outcome in the expectant management group, data from the MFMU Network's APEX study were evaluated. APEX was an observational study of approximately one-third of all deliveries at 25 hospitals in the MFMU Network, collected over a three-year period. For this analysis only nulliparous women with a singleton pregnancy delivered at 39 weeks 0 days to 42 weeks 0 days were included; those with diabetes, hypertension before 38 weeks, previa and abruption were excluded, yielding a cohort of 24,683 women. A composite outcome as close as possible to the proposed composite primary outcome for this trial was evaluated in these women. However, APEX only included pregnancies with fetal heart tones on admission for delivery and therefore stillbirth would be slightly underestimated. In addition, presence of thick meconium was used as a surrogate for meconium aspiration syndrome. The outcome rate in this cohort was 2.3% excluding presence of thick meconium; with thick meconium present the outcome rate was 9.3%. The real primary outcome rate could be expected to be between these two estimates.

Also, among women in the FOX trial, risks of adverse neonatal outcome at term (neonatal composite outcome including death, respiratory distress, seizure, sepsis, intubation and ventilator support, 5 minute Apgar score of 3 or less or hypoxic ischemic encephalopathy) were 3.7% at 36-38 weeks, 3.5% at 39 weeks, 3.8% at 40 weeks and 5.0% at ≥ 41 weeks.³⁸

Therefore the neonatal composite outcome rate for pregnancies expectantly managed beyond 39 weeks would be expected to be between 3.5% and 5%. This is consistent with other literature presented in Chapter 1.

5.2 Sample Size and Power

5.2.1 Primary Outcome

Table 6 shows the sample sizes per group (rounded up to the next 10) to detect a 35-40% reduction in the primary outcome, with 80% to 90% power, assuming type I error of 5% 2-sided and primary outcome rate in the expectant management arm between 3.5% and 5%. Some women will labor after randomization but prior to when their randomized assignment could be implemented (i.e., before 39 weeks). In addition, some women may undergo an elective induction off-protocol before 40 weeks, 5 days without a specific indication. These 'crossovers' would therefore behave more like the elective induction group; and it is assumed that their primary outcome rate would be the same as that of the elective induction group. This has the effect of reducing the effect size slightly depending on the proportion of crossovers: for example with 5% crossovers, the 40% nominal reduction becomes 39%.

Sample sizes were adjusted to take into account that between 5 and 10% of the women in the expectant management group will behave more like the elective induction group. The actual effect sizes are shown in parentheses in the table.

Data from observational studies suggest that a policy of induction of labor at 39 weeks may result in an equivalent reduction in adverse outcome.^{6,46} Using a type I error of 5% 2-sided and power of 85%, and an estimate that 7.5% of women in the expectant management group will be crossovers, 3000 women in each group (total N= 6000) would be needed to detect the actual reduction in primary outcome of 38%.

If the primary outcome rate is as high as 5%, a sample size of 6000 patients is sufficient to detect a 33-34% reduction in the primary outcome with at least 85% power, again assuming that 7.5% of women will be crossovers.

Table 6. Sample Sizes per Group for Different Primary Outcome Rates, Power and Effect Sizes

Reduction in Primary Outcome Rate (Reduction Adjusted for Crossover)	Power %	Nominal Primary Outcome Rate in Expectant Management Group			
		3.5%	4.0%	4.5%	5.0%
0% Crossover					
35% (35%)	80	3030	2650	2350	2120
	85	3460	3030	2690	2420
	90	4050	3540	3150	2840
40% (40%)	80	2250	1970	1750	1570
	85	2570	2250	2000	1800
	90	3010	2630	2340	2110
5% Crossover					
35% (33.8%)	80	3320	2900	2580	2320
	85	3790	3320	2950	2660
	90	4440	3880	3450	3110
40% (38.8%)	80	2460	2150	1910	1720
	85	2810	2460	2190	1970
	90	3290	2880	2560	2300
7.5% Crossover					
35% (33.2%)	80	3480	3040	2710	2440
	85	3980	3480	3100	2790
	90	4660	4070	3620	3260
40% (38.1%)	80	2580	2260	2010	1810
	85	2950	2580	2290	2060
	90	3450	3020	2680	2420
10% Crossover					
35% (32.6%)	80	3650	3200	2840	2560
	85	4180	3660	3250	2930
	90	4890	4280	3810	3430
40% (37.5%)	80	2700	2370	2100	1890
	85	3090	2710	2410	2170
	90	3620	3170	2820	2530

5.2.2 Cesarean Delivery

Assuming that the rate of cesarean delivery is 30% in the expectant management group, a sample size of 6000 women also yields more than 90% power to detect a nominal 15% increase or decrease even after adjusting for 7.5% crossovers.

5.3 Feasibility

Given that the sample size estimates are based on a composite of rare outcomes, it is planned that the primary outcome rate in the expectant management group be examined in the first 1000 patients. These data would be presented to the DSMC before any comparison by group, and the committee would be charged with making a recommendation regarding potential revision of the sample size in addition to addressing the feasibility of answering the primary research question.

5.4 Interim Analysis

The Data and Safety Monitoring Committee (DSMC) meets in person at least once per year and more often if recommended by the committee. Before each of the annual meetings, a formal detailed report will be written by the Biostatistical Coordinating Center (BCC) which presents all baseline variables, protocol adherence, side effects, all adverse events reported, as well as center performance in terms of recruitment, data quality, loss to follow-up and protocol violations.

Once sufficient patients have been accrued into the trial, the report will also include a formal interim analysis evaluating the primary outcome by treatment group. For this evaluation, a cohort of patients is chosen consisting of all patients randomized before a certain date so that the analysis cohort does not depend on gestational age at delivery.

The main statistical issue relevant to interim analysis is the problem of performing multiple tests of significance on accumulating data. For this trial, the group sequential method of Lan and DeMets will be used to characterize the rate at which the type I error is spent.⁵⁰ This method is flexible with regard to the timing of the interim analyses. Asymmetric stopping boundaries will be used for the Lan-deMets procedure. The upper boundary which describes the stopping rule for benefit will be based on 1-sided type I error of .025 and the Lan-deMets generalization of the O'Brien-Fleming boundary.

The lower boundary will be based on a less stringent stopping rule: 1-sided type I error of .05 and the Lan-deMets generalization of the Pocock type boundary.

It is often useful to calculate conditional power given the observed data to date, and conditional on the future data showing the originally assumed design effect. If this conditional power is low (under 10 percent) the DSMC may consider termination for futility if the accrual rate is slow, with confidence that the Type II error is not greatly inflated.⁵¹

It is recognized that any decision to terminate the study would not be reached solely on statistical grounds but on a number of complex clinical and statistical considerations.

5.5 Analysis Plan

All statistical analyses will be based upon the total cohort of patients randomized into the trial. Although data on some patients may be missing, all relevant data available from each patient will be employed in the analyses. Patients will be included in the treatment group to which they were randomly assigned regardless of compliance.

The primary analysis will consist of a simple comparison of binomial proportions. The relative risk and confidence interval will be reported. The individual components of the composite outcome will also be examined. If the treatment groups are found to differ on a pre-treatment factor known to be a risk factor for the outcome, the statistical analysis will adjust for these differences. An evaluation of treatment by center interaction will be included. An analysis adjusting by center also will be performed to ensure that center differences do not change the conclusion.

If the two groups show a difference in the incidence of the primary outcome or cesarean, interactions will be evaluated and subgroup analyses conducted to determine whether the effect prevails throughout

particular subgroups of patients. Indeed, NIH guidelines require investigators to evaluate consistency between the genders and across racial subgroups (see Section 5.5.1). It should be noted, however, that subgroup analyses have been greatly abused, particularly when there is no overall treatment difference.⁵² There is a strong temptation to search for a specific subpopulation in which the therapy is nevertheless effective. Yusuf et al. concluded “*the overall ‘average’ result of a randomized clinical trial is usually a more reliable estimate of the treatment effect in the various subgroups examined than are the observed effects in individual subgroups.*”⁵³ Thus subgroup analyses will be interpreted with care.

It is generally acknowledged that subgroup analysis that is pre-specified in the protocol has more validity than ad-hoc comparisons. The following factors will be considered for subgroup analysis, if there is a significant interaction between the factor of interest and the treatment effect.

- Race/ethnicity (see below)
- Modified Bishop score (< 5 and ≥ 5)
- Body mass index (obese and non-obese)
- Maternal age (< 35 and ≥ 35 years)
- Admitting provider specialty (see below)

Loss to follow-up will be defined as no information regarding stillbirth or neonatal outcome. There should be a low loss to follow-up rate. It is possible that a woman would deliver at a non-Network hospital; however, a record release will be obtained at enrollment to ensure that delivery and neonatal information can be obtained. However, to determine whether the results are robust, a sensitivity analysis will be performed including patients lost to follow up with different assumptions regarding their outcome.

Since many of the secondary endpoints are dichotomous variables like the primary outcome, standard statistical methods for rates and proportions will be appropriate. The Wilcoxon rank sum test will be used to compare continuous variables, and survival analysis methodology may be used to compare time-to-event variables.

In general, analyses of data will be conducted to address the primary and secondary research questions of the trial, and other interrelationships among elements of study data of interest to the investigators and of relevance to the objectives of the study.

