7.1.2 Biostatistical Coordinating Center

The BCC is responsible for all aspects of biostatistical design, data management, interim and final statistical analyses, and preparation of publications based on the study results. The Principal Investigator of the BCC reports to the Steering Committee and the Data and Safety Monitoring Committee.

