7.2.4 Data and Safety Monitoring Committee

The Data and Safety Monitoring Committee (DSMC), a group of individuals not affiliated with any of the participating institutions, was established by the NICHD. Before the trial can begin, the protocol must be approved by the committee. During the conduct of the study, the committee is charged with monitoring the emerging results for efficacy and safety, in addition to center performance and protocol adherence. Recommendations by the committee can include protocol modification, early termination for efficacy, or for unexpected safety problems. Recommendations are made to the NICHD and disseminated to the Steering Committee.

8 Study Timetable

Figure 1. Timetable

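### Does Section 5.5 need its own significance level and interval coverage for the final primary test?

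*Combined protocol and SAP*

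**What the plan says.** Section 5.5 (Analysis Plan) describes the final test in these words: "The primary analysis will consist of a simple comparison of binomial proportions. The relative risk and confidence interval will be reported". The next paragraph sets a condition for subgroup work: "If the two groups show a difference in the incidence of the primary outcome or cesarean, interactions will be evaluated and subgroup analyses conducted". Neither sentence carries a level, and Section 5.5 does not mention interim looks.

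The error rates are elsewhere:

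- Section 5.2.1 and Appendix A set type I error at 5% two-sided.
- Section 5.4 plans "a formal interim analysis evaluating the primary outcome by treatment group" under a Lan-DeMets group sequential method. "The upper boundary which describes the stopping rule for benefit will be based on 1-sided type I error of .025", with an O'Brien-Fleming-type function.
- On the other side, "The lower boundary will be based on a less stringent stopping rule: 1-sided type I error of .05", with a Pocock-type function.
- On schedule, Section 5.4 says only: "This method is flexible with regard to the timing of the interim analyses".
- Section 7.1.2 puts both analyses in one place: "The BCC is responsible for all aspects of biostatistical design, data management, interim and final statistical analyses".

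**The concern.** After interim looks, the critical value left for the final test is larger than 1.96. If Section 5.5 is read alone, an analyst could test at 1.96 and report an ordinary 95% interval, or use the value left by Section 5.4. On a borderline result these can disagree: the 95% interval for the relative risk excludes 1, yet the benefit boundary is not met. The report could then be worded either way after the data are seen.

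The same silence affects the condition for subgroup analyses. It rests on a difference in the primary outcome or cesarean with no stated standard, and the interim plan covers only the primary outcome. At stake would be a slightly inflated false-benefit error and an unclear entry condition for subgroup work.

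**Working it through.** **1. The plan's own figure.** Inputs from Section 5.2.1 and Table 6: expectant rate 3.5%, nominal reduction 40% (induction rate 2.1%), 7.5% crossover, 5% two-sided, 85% power. (Appendix A prints 2.28% for induction, which is 1 − 2.28/3.5 = 34.9% and not 38%. That is a separate matter, so I use Table 6.)

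- Expectant rate after crossover: 0.925 × 0.035 + 0.075 × 0.021 = 0.03395. Reduction: 1 − 0.021/0.03395 = 38.1%, as in Table 6.
- n = [1.960 √(2p̄(1−p̄)) + 1.036 √(p₁(1−p₁) + p₂(1−p₂))]² / (p₁−p₂)², with p̄ = 0.027475 and p₁−p₂ = 0.01295. This gives 2860 per group.
- With continuity correction, n/4 × [1 + √(1 + 4/(n × 0.01295))]² = 3012.

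Table 6 has 2950 and the text 3000, so the design rests on 5% two-sided. The benefit side of Section 5.4, one-sided .025, is half of that.

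**2. What Section 5.4 leaves for the final test.** The function is α(t) = 2[1 − Φ(2.241/√t)], where 2.241 is the upper 0.0125 normal point. For one look at half the information, α(0.5) = 0.0015, so the first boundary is 2.963. The final value c solves P(Z₁ < 2.963, Z₂ ≥ c) = 0.025 − 0.0015, giving c = 1.969. Other schedules follow by recursive integration. All schedules are assumptions, and the lower boundary is left out of the benefit-side calculation.

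| Interim looks | Final value | Two-sided level | One-sided error if 1.96 is used |
|---|---|---|---|
| 1 at 25% | 1.960 | 0.0500 | 0.0250 |
| 1 at 50% | 1.969 | 0.0490 | 0.0255 |
| 2 equally spaced | 1.993 | 0.0463 | 0.0268 |
| 3 equally spaced | 2.014 | 0.0440 | 0.0277 |
| 4 equally spaced | 2.031 | 0.0423 | 0.0283 |
| 50% and 90% | 2.057 | 0.0397 | 0.0288 |
| 80% and 90% | 2.072 | 0.0383 | 0.0293 |

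The matching interval coverage runs from 95.0% to 96.2%. Power at 3000 per group, counting early crossings, stays at about 86% or slightly above throughout.

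**3. Size in events.** Take 76 induction and 102 expectant events, 3000 per group.

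- Pooled rate 178/6000 = 0.02967. z = (26/3000) / √(2 × 0.02967 × 0.97033/3000) = 1.978.
- RR = 76/102 = 0.745. SE of log RR = √(1/76 + 1/102 − 2/3000) = 0.1493.
- Upper limit: 0.745 × exp(1.96 × 0.1493) = 0.998. With 1.993 it is 1.003.

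This result passes 1.96 and the one-look boundary (1.969) but not the two-look boundary (1.993). Across 95 to 115 expectant events, the largest succeeding induction count differs by 0 or 1 for one to four equally spaced looks. For looks at 50% and 90% it differs by 2 at 96, 103, 110 and 111 expectant events.

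**4. Chance of landing in the gap.** Under no effect this is the last column minus 0.025, so 0 to 0.0043. Under the design effect it is 0.2% to 1.4% for one to four equally spaced looks and 1.6% for looks at 50% and 90%.

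**5. Level for cesarean.** Section 5.2.2 claims more than 90% power for a 15% change either way from 30%, with 7.5% crossover. The expectant rate becomes 0.925 × 0.30 + 0.075 × 0.255 = 0.2966 for a decrease and 0.925 × 0.30 + 0.075 × 0.345 = 0.3034 for an increase. Power is 95.0% and 93.1% at 5% two-sided, but 91.4% and 88.6% at 2.5%. Only 5% fits the claim in both directions.

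**The case for a change.** The best case for a change is that the link costs one sentence and would settle a reporting choice before a borderline result is seen. The documents do contain the ingredients of two final critical values, 1.96 from a plain 5% test and something larger from Section 5.4. A number could not be fixed in advance, because timing is flexible, but a reference could. For cesarean, Section 5.4 supplies nothing at all.

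It is true that Section 5.5 is silent. The rest is weaker than it appears:

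- A spending function allocates the whole error, including the share kept for the last analysis. Naming it in Section 5.4 therefore specifies the final benefit test. Section 5.5 states no rival rule: no 1.96, no 95%, no p-value threshold.
- Reading Section 5.5 as an unadjusted test assumes that one coordinating center would spend alpha at the looks and forget it at the end.
- Matching the interval's coverage to the boundary is one convention. A labelled 95% interval beside the boundary decision is equally sound, so leaving coverage open costs nothing inferentially.
- The subgroup step has a second condition. Section 5.5 also requires a significant interaction, and Section 5.5.2 repeats this for provider specialty. The cesarean level can be recovered from Section 5.2.
- The lower boundary adds no ambiguity. Futility is handled separately by conditional power, and Section 7.2.4 says of the monitoring committee: "Recommendations by the committee can include protocol modification, early termination for efficacy, or for unexpected safety problems". Harm is the sensible reading of that boundary.

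**Conclusion.** No change is needed. The omission in Section 5.5 is real but editorial. The final benefit test follows from Section 5.4 once the looks are known, within the 5% two-sided total of Section 5.2.1 and Appendix A. Followed as written, the plan controls false-benefit error at one-sided .025 and leaves sample size, power and the efficacy conclusion as they are.

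Even if the looks were ignored at the end, the one-sided error would be about 0.025 to 0.029 and the threshold would move by 0 to 2 events. These figures are illustrative: they depend on assumed look schedules, on 3000 per group, on the Table 6 rates and on 95 to 115 expectant events. A later or more frequent schedule could move them slightly further. The conclusion does not depend on them, because it rests on Section 5.4 being applied to the final test as well as the interim ones.

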3.6 Randomization Method

Randomization for consenting women will occur at 38 weeks 0 days to 38 weeks 6 days of gestation. Consenting women will be assigned to induction of labor at 39 weeks 0 days to 39 weeks 4 days or expectant management in a 1:1 ratio according to a randomization sequence prepared and maintained centrally by the Biostatistical Coordinating Center (BCC).

The simple urn method will be used to generate the randomization sequences because it provides a high probability of balance in treatment assignments, it is unpredictable, and it allows an explicit randomization analysis to be conducted with relative ease.⁴⁸ Randomization will be stratified by clinical site to assure balance between the two treatment groups with respect to anticipated differences in the clinic populations and possible differences in patient management.

4 Study Procedures

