5.5.2 Admitting Provider Specialty Subgroup Analysis

Although admitting provider specialty is not a baseline variable, this variable will be evaluated for subgroup analysis if the two groups show a difference in the incidence of the primary outcome or cesarean, and if the test for interaction is significant. Elective induction of labor may be perceived as an intervention more likely utilized by obstetricians than by midwives, therefore it is important to demonstrate whether a treatment effect is present among patients treated by obstetricians and among patients treated by midwives.

6 Data Collection

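### Section 5.5 lets observed imbalance select among known risk factors for adjustment and gives the adjusted result no status; as a minor second point, the primary test omits the site strata

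*Combined protocol and SAP*

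**What the plan says.** Section 5.5 states: "The primary analysis will consist of a simple comparison of binomial proportions". It continues, with no condition attached: "The relative risk and confidence interval will be reported".

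A conditional rule follows: "If the treatment groups are found to differ on a pre-treatment factor known to be a risk factor for the outcome", covariate adjustment is to be made. Two things must hold: the factor is already known to carry risk, and the arms are seen to differ on it. The section does not list the factors, define what counts as a difference, name a model, or give the adjusted result a status.

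On center, the same paragraph plans an interaction evaluation and says: "An analysis adjusting by center also will be performed to ensure that center differences do not change the conclusion". Section 3.6 says: "Randomization will be stratified by clinical site to assure balance between the two treatment groups".

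Section 4.3 lists the baseline items available, among them "Demographic information: age, race, ethnicity, insurance status" and "Medical history: first clinic weight, current weight, height, chronic disease history".

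The original and the amended protocol carry the same adjustment rule, and none of the three listed modifications touches it.

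**The concern.** In a randomized trial, a baseline difference between arms is due to chance. Its size says little about whether adjusting for the factor will sharpen the estimate; expected prognostic strength is the better guide, and it can be judged in advance. Section 5.5 accepts this principle for subgroups, where it prefers pre-specified factors and lists them, but gives no such list for covariates.

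The missing status matters because the center sentence shows how the plan words a check: it is an additional analysis with a stated purpose. The imbalance sentence has neither feature.

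The open choices would count mainly when a result lies near the threshold. The Biostatistical Coordinating Center prepares the interim comparison by arm (Section 5.4) and runs the final analysis (Section 7.1.2), so the choices could fall to a unit that has seen outcomes by arm. Nothing suggests misuse; a fixed list and a stated status simply remove the question.

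Separately, a test that leaves out a stratification factor can be slightly conservative and lose a little power if sites differ in risk.

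**Working it through.** **1. The plan's own figure.** Inputs from Section 5.2.1: 3.5% nominal rate under expectant management, 40% nominal reduction, 7.5% crossover, two-sided 5% type I error, 85% power.

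- Induction rate: 0.60 × 3.5% = 2.1%.
- Expectant management after crossover: 0.925 × 3.5% + 0.075 × 2.1% = 3.395%.
- Reduction: 1 − 2.1/3.395 = 38.1%, as in Table 6.
- Per arm, n = [z(0.975)·√(2·p̄·q̄) + z(0.85)·√(p₁q₁ + p₂q₂)]² / (p₁ − p₂)², with p̄ = 2.7475%. This is (0.4531 + 0.2394)² / 0.01295² ≈ 2860, or 3012 with continuity correction. Table 6 has 2950 and the text 3000.
- Power at 3000 per arm, uncorrected: 86.6%.

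The design reproduces. For the nominal 35% reduction the rates are 3.408% and 2.275% (33.2%), with power 75.2%.

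**2. How often the rule would fire.** The documents define no criterion. Assume that p < 0.05 counts as a difference and that k independent factors are examined. The chance of at least one flag is 1 − 0.95^k: 14.3% for k = 3, 18.5% for 4, 22.6% for 5.

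**3. What it does to the result.** Simulation with 3000 per arm and 200,000 replicates per setting. Assumed: 3 to 5 binary factors, prevalence 10% to 60%, covariate relative risk 1.5 to 3. The adjusted analysis is modified Poisson regression with robust variance on the flagged factors.

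| True effect | Simple and triggered verdicts differ (all trials) |
|---|---|
| None | 0.1% to 0.6% |
| 38.1% reduction | 0.2% to 1.0% |
| 33.2% reduction | 0.4% to 1.5% |

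When the rule fires, the relative risk moves by a median of 1.1% to 3.1% (95th percentile 2.0% to 5.5%). Taking the better of the two results moves type I error from 4.89% to 4.95% in the setting with the smallest gap and from 5.08% to 5.32% in the largest, so 0.1 to 0.2 points.

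A second simulation used logistic adjustment, 1 to 5 factors of 30% prevalence and odds ratios of 1.5 to 3. If the triggered result mechanically replaced the simple one, type I error was 4.7% to 5.1%. Verdicts differed in at most 1.1% of trials.

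**4. An adjusted analysis that is always run.** In the setting of step 3, with all k covariates, type I error is 4.8% to 5.0%. Power at the 38.1% effect is 87.0% to 88.9%, against 87.0% to 87.1% for the simple test, with no gain at covariate relative risk 1.5.

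It disagrees with the simple test more often than the triggered rule does (3,000 replicates per setting, 38.1% effect):

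| Covariates, relative risk | Triggered vs simple | Always-run vs simple |
|---|---|---|
| 3, 1.5 | 0.3% | 0.8% |
| 4, 2 | 0.5% | 2.1% |
| 5, 3 | 0.9% | 3.9% |

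If both results were available with no stated order and the better one were taken, type I error would be 5.2% to 6.5%.

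**5. Site strata.** Assumed: 16 centers (the number listed in the amended Appendix A), 4:1 largest to smallest, site log-odds SD 0 to 1.0, overall expectant-management rate held at 3.395%.

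| Site SD | Power, pooled / stratified | Type I error, pooled / stratified |
|---|---|---|
| 0 | 87.0% / 87.0% | 4.98% / 4.98% |
| 0.5 | 87.2% / 87.3% | 4.88% / 4.98% |
| 1.0 | 87.3% / 87.8% | 4.51% / 4.91% |

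Under the 38.1% effect, verdicts differ in 0.02% to 0.6% of trials. For cesarean (29.66% vs 25.5%, site SD 0 to 0.5) the gain is 0 to 0.4 points.

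**The case against.** The strongest reply is that little is left open. The primary analysis is named without condition. The rule already requires that a factor be a known risk factor, so imbalance only narrows a prognostic set. The error rates barely move. Center is covered by an adjusted analysis and an interaction evaluation. One sentence saying that the simple comparison alone is confirmatory would do the protective work, whereas an always-run model produces more discordant pairs than the rule it replaces.

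Most of this stands, and it sets the size of the point. The label matters more than the model. What remains is that imbalance is a poor selector among known risk factors, and that the text does not give the label.

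Two further cautions also stand. The Section 5.5 subgroup list should not simply be borrowed as the covariate list, because it was not drawn up for prognosis of the neonatal composite. Also, Section 4.1 allows the cervical exam up to 24 hours after randomization in a trial that Appendix A calls unmasked. Some modified Bishop scores may therefore be recorded with the allocation known, although Section 4.3 lists the score among the items obtained at randomization.

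A reader might infer that an adjusted result may displace the primary one, that the false-positive rate is materially inflated, or that center is ignored. The documents support none of these: the primary comparison is stated outright, the calculations show type I error near 5%, and center adjustment is planned.

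**Conclusion.** The point holds as a cheap improvement to consider. Nothing in the plan as written is invalid, and the sample size does not change. The wording gap is certain; its numerical effect rests on assumed inputs (a p < 0.05 trigger, number and prevalence of factors, covariate strength, variation between sites), because the documents give none of them. Within those ranges the consequence of the rule is confined to results near the threshold.

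The strata point is minor. The top of its range needs a site log-odds SD of 1.0, which is roughly a 50-fold 95% range in odds between sites (e^(2 × 1.96) ≈ 50). It would be wrong to conclude that the unstratified test is invalid: it is at most slightly conservative.

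**What to change.** **(1) Covariate adjustment.** Delete the imbalance trigger. State that the primary comparison alone is confirmatory, whatever imbalance is seen. Add one adjusted relative-risk analysis, for example modified Poisson regression with robust variance, that is run in every case and labelled supportive.

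Fix its covariates in advance for their expected prognostic value for the neonatal composite, from items already collected under Section 4.3. Maternal age and body mass index are candidates; since two weights are recorded, say which one defines body mass index. Use modified Bishop score only if the exam preceded randomization. Leave out admitting provider specialty, since Section 5.5.2 says: "Although admitting provider specialty is not a baseline variable". Settle the list before any further unblinded look, through people who have not seen outcomes by arm.

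**(2) Strata (minor).** If no unblinded comparison of the primary outcome has been made, make the Cochran-Mantel-Haenszel test and Mantel-Haenszel relative risk, stratified by the randomization site, the primary analysis at interim and final, with the simple comparison as sensitivity. Otherwise keep the simple test and run the planned center-adjusted analysis on the randomization strata. The documents plan interim comparisons but do not say whether one has taken place; changing the primary test after one would cost more than it gains.

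**Cost.** A short change to Section 5.5 and no new data. Section 1.3 requires Steering Committee and IRB approval, and DSMC approval if the change is judged major.
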